## 9.2.8 Adverse Events by Maximum Relationship

TEAEs will also be summarized by maximum relationship to treatment, as assessed by the investigator, by "as treated" treatment group and overall. If a subject has a TEAE with an unknown relationship, then the subject will be counted in the relationship category of "unknown," even if the subject has another occurrence of the same event with a relationship present. The only exception is if the subject has another occurrence of the

same TEAE with a relationship assessment of "reasonable possibility." In this case, the subject will be counted under the "reasonable possibility" category.

### 9.2.9 Adverse Events by "Reasonably Possibly Related" Relationship

TEAEs and reasonably possibly related AEs occurring for more than 2% of the subjects in any of the treatment groups will also be summarized by MedDRA SOC and PT. If a subject has an AE with an unknown relationship, then the subject will be counted in as 'related.'

#### 9.2.10 Frequent (> 5%) Adverse Events and Reasonably Possibly Related Adverse Events by Preferred Term in Decreasing Frequency

TEAEs and reasonably possibly related AEs occurring for more than 5% of the subjects in any of the treatment arms will be summarized by MedDRA PT in decreasing frequency separately.

## 9.2.11 Listing of Adverse Events

The following additional summaries of AEs will be prepared.

- Listing of Subjects with Treatment-Emergent AESIs
- Listing of Subjects with Pretreatment SAEs
- Listing of Subjects with Treatment-Emergent SAEs
- Listing of all AEs that led to discontinuation of study drug
- Listing of all deaths.

## 9.3 Analysis of Laboratory Data

Data collected from central and local laboratories, including additional laboratory testing due to an SAE, will be used in all analyses, except for Baseline, where SAE-related laboratory assessments on or before the first dose of study drug will be excluded. The

clinical laboratory tests defined in the protocol operations manual (e.g., hematology and clinical chemistry) will be summarized.

Mean change from baseline to each applicable post-baseline visit will be summarized for selected laboratory variables, with the number of observations, baseline mean, and visit mean. The change from baseline mean, standard error, and 95% confidence interval will be presented for the mean change from baseline within each treatment group and difference between treatment groups using ANOVA model.

The baseline and post-baseline laboratory observations will be categorized as Grade 1, Grade 2, Grade 3, and Grade 4 according to OMERACT criteria (Rheumatology Common Toxicity Criteria v.2.0). For creatine phosphokinase and creatinine, NCI CTC criteria will be used.

For each laboratory variable, shift tables will be generated that cross tabulate the subjects' as deemed appropriate by "as treated" treatment group:

- Category of the baseline value versus category of the final value.
- Category of the baseline value versus maximum category.
- Category of the baseline value versus minimum category.

Note that the minimum/maximum category is used, rather than the category of the minimum/maximum value. The two may be different due to variation in the reference range.

No statistical tests will be performed for this analysis.

Laboratory abnormalities will be evaluated based on Potentially Clinically Significant (PCS) criteria (Appendix C). For each laboratory PCS criterion, the number and percentage of subjects who have a laboratory value meeting the criteria will be summarized. Listings will be provided to summarize subject-level laboratory data for subjects meeting PCS criteria.

According to FDA's Guidance for Industry "Drug-Induced Liver Injury: Premarketing clinical evaluation" (July 2009), when aminotransferase (AT) abnormalities indicating hepatocellular injury are accompanied by evidence of impaired hepatic function (bilirubin elevation  $> 2 \times ULN$ ), in the absence of evidence of biliary obstruction (i.e., significant elevation of ALP) or some other explanation of the injury (e.g., viral hepatitis, alcohol hepatitis), the combined finding (i.e., Hy's Law cases) represents a signal of a potential for the drug to cause severe DILI.

For the purpose of assessing for potential Hy's law cases, the frequencies and percentages of subjects with post baseline liver-specific function test values that meet the following criteria of potential clinical interest will be summarized by "as treated" treatment group:

- ALT  $\geq$  3 × ULN
- ALT  $\geq$  5 × ULN
- ALT  $\geq 10 \times ULN$
- ALT  $\geq 20 \times ULN$
- AST  $\geq$  3 × ULN
- AST  $\geq$  5  $\times$  ULN
- AST  $\geq 10 \times ULN$
- AST  $\geq 20 \times ULN$
- Total Bilirubin Level (TBL)  $\geq 2 \times ULN$
- Alkaline phosphatase  $\geq 1.5 \times ULN$
- ALT and/or AST  $\ge$  3 × ULN and concurrent TBL  $\ge$  1.5 × ULN
- ALT and/or AST  $\geq$  3 × ULN and concurrent TBL  $\geq$  2 × ULN

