4 INVESTIGATIONAL PLAN

4.1 Overall Study Design and Plan

This is a 12-week, randomized, double-blind, parallel-group, Phase 2, dose exploratory, multicenter study designed to assess the safety and efficacy of ABBV-105 and ABBV-599 in subjects with active RA who have had inadequate response to bDMARD therapy and are on stable background csDMARD treatment. Subjects who meet eligibility criteria will be randomized in a 3:2:2:2:2:1 ratio to 1 of 6 treatment groups:

- Group 1: Upadacitinib 15 mg and ABBV-105 60 mg administered once daily (QD) (n = 60)
- Group 2: ABBV-105 60 mg and upadacitinib placebo QD (n = 40)
- Group 3: ABBV-105 20 mg and upadacitinib placebo QD (n = 40)
- Group 4: ABBV-105 5 mg and upadacitinib placebo QD (n = 40)

- Group 5: Upadacitinib 15 mg and ABBV-105 placebo QD (n = 40)
- Group 6: ABBV-105 placebo and upadacitinib placebo QD (n = 20)

The study duration will include a 35-day maximum screening period and a 12-week randomized, double blind, parallel-group treatment period with 30-day follow-up. Study visits will be conducted at Screening, Baseline, Week 2, Week 4, Week 8, and Week 12. For post-baseline visits, a visit window of \pm 3 days will be allowed.

The schematic of the study is shown in Figure 1.

The study population will consist of adult subjects who are at least 18 years of age with a diagnosis of RA for \geq 3 months and also fulfill the 2010 ACR/EULAR classification criteria for RA. Subjects will have been treated for \geq 3 months with \geq one bDMARD but continue to exhibit active RA or had to discontinue bDMARD(s) due to intolerability or toxicity, irrespective of treatment duration.

Randomization will be stratified by number of prior bDMARDs used (failed 1 or 2 biologics with the same mechanism of action; failed \geq 3 biologics with the same mechanism of action and/or \geq 2 bDMARDs with different mechanisms of action). Once approximately 35% of the total subjects have been randomized to the second stratum, further screening of subjects in that group may be suspended. See Section 5.1 for information regarding eligibility criteria.

This study will be conducted in approximately 240 subjects with-planned interim safety reviews as discussed in Section 7.5.

Figure 1. Study Design

QD = once daily

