5.6 Follow-Up for Subject Withdrawal from Study

To minimize missing data for efficacy and safety assessments, subjects who prematurely discontinue study drug treatment should continue to be followed for all regularly scheduled visits, unless subjects have decided to discontinue the study participation entirely (withdrawal of informed consent). Subjects should be advised on the continued scientific importance of their data even if they discontinue treatment with study drug early.

If a subject prematurely discontinues study participation (withdrawal of informed consent), the procedures outlined for the PD visit should be completed as soon as possible, preferably within 2 weeks. In addition, if subject is willing, a 30-day follow-up phone call after the last dose of study drug may be completed to ensure all treatment-emergent AEs/SAEs have been resolved.

All attempts must be made to determine the date of the last study drug dose and the primary reason for discontinuation of study drug or study participation. The information will be recorded on the appropriate electronic case report form (eCRF) page. However, these procedures should not interfere with the initiation of any new treatments or therapeutic modalities that the Investigator feels are necessary to treat the subject's condition. Following discontinuation of study drug, the subject should be treated in accordance with the Investigator's best clinical judgment irrespective of whether the subject decides to continue participation in the study.

If a subject withdraws from the main study, biomarker research samples will continue to be stored and analyzed. A subject must contact the study investigator if they no longer want their samples to be stored and analyzed. Once AbbVie is notified, no new information will be collected, no new analysis will be started, and the samples will be destroyed unless a regulatory authority requires AbbVie to keep them. However, if AbbVie (or people or companies working with AbbVie) collected any information or did any testing before withdrawal, AbbVie (or people or companies working with AbbVie) will still use and disclose such information, use the test results, and keep the data generated from the samples.

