6.2 Toxicity Management

The management of specific AEs and laboratory parameters is described in Table 4 and in the Operations Manual.

The toxicity management of the AEs including AESI consists of safety monitoring (review of AEs on an ongoing basis, and periodical/ad hoc review of safety issues by a safety data monitoring committee), interruption of study drug dosing with appropriate clinical management if applicable, and discontinuation of the subjects from study drug. The management of specific AEs and laboratory parameters is described below.

For subjects who discontinue study drug but continue study participation and are on standard of care therapies, these toxicity management requirements do not apply (including alerts from the central lab) and any intolerability to standard of care therapies should be managed by the prescribing physician.

Serious Infections: Subjects should be closely monitored for the development of signs and symptoms of infection during and after treatment with study drug. Study drug should be interrupted if a subject develops a serious infection or an opportunistic infection. A subject who develops a new infection during treatment with study drug should undergo prompt diagnostic testing appropriate for an immunocompromised subject. As appropriate, antimicrobial therapy should be initiated, and the subject should be closely monitored. Study drug may be restarted once the infection has been successfully treated. Subjects who develop active TB or experience hepatitis B reactivation must be discontinued from study drug. To further monitor subjects for serious infections, subjects will complete at-home weekly temperature monitoring. If above 100.5 degrees Fahrenheit (38 degrees Celsius), subject should inform their study doctor to assess the need for further evaluation.

Canada only: Investigators should be advised to follow local public health guidelines in order to prevent subjects enrolled in these trials from acquiring TB.

Serious Gastrointestinal Events: Subjects presenting with the onset of signs or symptoms of a serious gastrointestinal event should be evaluated promptly for early identification of gastrointestinal perforation. If the diagnosis of gastrointestinal perforation is confirmed, the subject must be discontinued from study drug.

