#### 9.4 Analysis of Vital Signs

Vital sign variables include sitting systolic blood pressure, sitting diastolic blood pressure, pulse, body temperature, and weight. The criteria for potentially clinically significant vital sign findings are presented in Appendix C.

A treatment-emergent value is defined as a value with a date that is on or after the first dose of study drug, and no more than 30 days after the last dose of study drug.

The change from baseline mean, standard error, and 95% confidence interval will be presented for the mean change from baseline within each treatment group and difference between treatment groups using ANOVA model.

Vital sign variables will be evaluated based on potentially clinically significant (PCS) criteria (Appendix C). For each vital sign PCS criterion, the number and percentage of subjects who have a vital sign value meeting the criteria will be summarized. Listings will be provided to summarize subject-level vital sign data for subjects meeting PCS criteria.

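### SAP 9.3 puts no off-drug limit on laboratory values, so results from up to about 12 weeks after the last dose can enter the shift, PCS and liver tables of the treatment received

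*SAP*

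**What the plan says.** On which laboratory results count, SAP 9.3 states: "Data collected from central and local laboratories, including additional laboratory testing due to an SAE, will be used in all analyses". The one exception removes SAE-related tests from Baseline. The outputs that follow are mean change by visit, shift tables, PCS counts and the liver (potential Hy's law) table, and none has a date limit. One shift table is "Category of the baseline value versus category of the final value"; the other two use the maximum and minimum category. The liver table counts "subjects with post baseline liver-specific function test values that meet the following criteria of potential clinical interest".

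On follow-up, protocol 5.6 states that "subjects who prematurely discontinue study drug treatment should continue to be followed for all regularly scheduled visits", unless they withdraw consent. Protocol 6.2 adds: "For subjects who discontinue study drug but continue study participation and are on standard of care therapies, these toxicity management requirements do not apply". Central-laboratory alerts are switched off for them as well.

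Elsewhere the SAP does set time limits. Section 9.2.1 restricts treatment-emergent adverse events to 30 days after the last dose. Section 9.4 defines a treatment-emergent value as one dated "on or after the first dose of study drug, and no more than 30 days after the last dose of study drug". Safety results are grouped by treatment received (SAP 4.0), taken as the most frequent regimen (SAP 9.1).

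**The concern.** A subject who stops early, starts another therapy and keeps attending will have blood drawn at the remaining visits. Under 9.3 those results are tabulated under the study treatment received. An ALT rise or a low cell count caused by the later therapy would then appear as a finding for ABBV-105, ABBV-599, upadacitinib or placebo. Conversely, a subject who stopped because of a laboratory abnormality and then recovered can show a normal final value.

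Anemia, neutropenia, lymphopenia, raised CPK, raised creatinine and hepatic events are adverse events of special interest (protocol 6.1). The same abnormality, seen 50 days after the last dose, would count in the laboratory table but not in the adverse event table. The trial is meant to inform the choice of dose for further development, so laboratory safety by arm will be read closely, and the most serious categories will hold few cases.

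**Working it through.** The documents give no figure for time off drug, so there is nothing to reproduce. The check compares the rules and then does the calendar arithmetic.

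**1. Rules side by side**

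| Data | SAP section | Limit after last dose | Used by the outputs? |
|---|---|---|---|
| Adverse events | 9.2.1 | 30 days | Yes |
| Vital signs | 9.4 | 30 days, in a definition | No: mean change, PCS counts and listings do not use the term |
| Laboratory | 9.3 | None | Not applicable |
| ECG | 9.6 | None | Not applicable |
| Continuous efficacy (MMRM) | 8.2, 8.3.5.1 | Data after stopping set to missing | Yes |

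**2. Calendar**

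Inputs: first dose on Day 1 (protocol 5.7); "Study visits will be conducted at Screening, Baseline, Week 2, Week 4, Week 8, and Week 12" with a window of plus or minus 3 days (protocol 4.1); hematology and chemistry at each of these visits (protocol Appendix D).

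Visit day = 7 × week + 1, giving Days 15, 29, 57 and 85. These match the exposure cut points in SAP 6.0. Days off drug = visit day − day of last dose.

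| Last dose | Week 4 (Day 29) | Week 8 (Day 57) | Week 12 (Day 85) | Week 12 at +3 days |
|---|---|---|---|---|
| Day 1 | 28 | 56 | 84 | 87 |
| Day 8 | 21 | 49 | 77 | 80 |
| Day 15 | 14 | 42 | 70 | 73 |
| Day 29 | 0 | 28 | 56 | 59 |
| Day 54 | – | 3 | 31 | 34 |
| Day 55 | – | 2 | 30 | 33 |

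The longest scheduled lag is 84 days (84/7 = 12.0 weeks), or 87 days (12.4 weeks) with the window.

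The nominal Week 12 sample falls more than 30 days after the last dose when that dose was on or before Day 85 − 31 = Day 54. For a visit at −3 days (Day 82) the limit is Day 51; at +3 days (Day 88) it is Day 57. The nominal Week 8 sample falls outside when the last dose was on or before Day 57 − 31 = Day 26.

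**3. Direction, by output**

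- Maximum and minimum category shifts, PCS counts, liver criteria: a further value can push an extreme outward or meet a threshold. It cannot undo one already reached on drug. The error can only add cases.
- Final-value shift and visit means: a late value replaces or joins the on-drug picture. Recovery can hide an effect, and a later therapy can create one.

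**4. Size of one added case**

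1/60 = 1.7% (ABBV-599); 1/40 = 2.5% (each ABBV-105 dose, upadacitinib); 1/20 = 5% (placebo).

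**5. With a 30-day limit**

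The longest counted lag falls from 84 to 30 days, removing up to 84 − 30 = 54 off-drug days (87 − 30 = 57 with the window). It does not remove everything: a subject whose last dose was on Day 15 still contributes the Week 4 sample, 14 days off drug.

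**The case against.** The strongest reply is that the sentence in 9.3 is about data source (central, local, SAE-driven), not timing. On this view the SAP is silent on off-drug values, and the 9.4 definition, which speaks of a value in general, was meant to cover laboratory data too. The version history supports that intention: its version 2.0 entry mentions a clarification of cut-off days for laboratory and vital sign values. This makes a shared limit plausible, but the current 9.3 neither uses the term nor points to 9.4. A programmer following it would include every post-baseline value.

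A second reply is that counting everything is conservative for safety. That is fair for the extreme-category, PCS and liver outputs, but not for the final-value shift or the means. Third, these are largely descriptive summaries in a 12-week Phase 2 trial: the shift tables carry no tests, PCS listings are planned, and a premature discontinuation visit should give a sample near stopping. This limits the consequence without settling which values belong in the tables.

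Four stronger readings are tempting and not supported:

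- That late values count against the randomised drug. Safety data are grouped by treatment received; the two coincide only for subjects given their assigned drug.
- That vital signs are already limited to 30 days. Section 9.4 defines the term and then does not use it.
- That recovery dilutes every laboratory output. It cannot remove cases from the extreme-category, PCS or liver counts.
- That the dilution of Week 12 means can be given a percentage. The documents state no stopping rate, and some who stop will withdraw consent and give no later samples.

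**Conclusion.** The point holds as a gap that should be closed. As written, laboratory values up to about 12 weeks after the last dose can be tabulated under the treatment received, against 30 days for adverse events. For the extreme-category shifts, PCS counts and liver criteria, the consequence is added cases not due to study drug. For the final-value shift and visit means, it can go either way.

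The 84-day figure assumes a last dose on Day 1 and a subject who stays in follow-up to Week 12. It covers scheduled samples only. How many subjects are affected depends on early stopping and on continued attendance, neither of which the documents quantify. The lag and the size of a single case are therefore firm, but the total effect is unknown.

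**What to change.** In SAP 9.3, state that post-baseline values in the shift tables, PCS counts and liver criteria are treatment-emergent values as defined in 9.4, that is, from the first dose through 30 days after the last. Make the same term operative in the 9.4 PCS counts and in the ECG summaries of 9.6. List later values separately.

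State also whether the by-visit means use this window. That is a separate choice: the window leaves fewer early stoppers in the Week 12 mean and still admits values from the first 30 days off drug, so it only partly deals with dilution.

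The cost is a few sentences and a date filter, with no new data. The downside is small: late-onset values move from the tables to the listings, where they remain visible.

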#### 2.3 Treatment Assignment and Blinding

Subjects who meet eligibility criteria will be randomized in a 3:2:2:2:2:1 ratio to 1 of 6 treatment groups:

- Group 1: Upadacitinib 15 mg and ABBV-105 60 mg once daily (QD) (n = 60)
- Group 2: ABBV-105 60 mg and upadacitinib placebo QD (n = 40)
- Group 3: ABBV-105 20 mg and upadacitinib placebo QD (n = 40)
- Group 4: ABBV-105 5 mg and upadacitinib placebo QD (n = 40)
- Group 5: Upadacitinib 15 mg and ABBV-105 placebo QD (n = 40)
- Group 6: ABBV-105 placebo and upadacitinib placebo QD (n = 20)

The study duration will include a 35-day maximum screening period; a 12-week randomized, double blind, parallel-group treatment period with 30-day follow-up. Study visits will be conducted at Screening, Baseline, Week 2, Week 4, Week 8 and Week 12. For post-baseline visits, a visit window of  $\pm$  3 days will be allowed.

Randomization will be stratified by number of prior bDMARDs used (failed 1 or 2 biologics with the same mechanism of action; failed  $\geq$  3 biologics with the same mechanism of action and/or  $\geq$  2 biologics with multiple mechanisms of action). Once approximately 35% of the total subjects have been randomized to the group who failed  $\geq$  3 biologics with the same mechanism of action and/or  $\geq$  2 biologics with multiple mechanisms of action.

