## 2.4 Sample Size Determination

The planned total sample size is 240. Forty (40) patients per arm of ABBV-105 can provide approximately 83% power to detect a –0.88 difference in DAS28 (CRP) change from baseline for ABBV-105 vs placebo combined with 20 borrowed historical placebo subjects (assuming a placebo mean change from baseline –0.77, and ABBV-105: –1.65 with common SD = 1.5) using two group t-test with one-sided significant level  $\alpha = 0.05$ . It can provide a minimum of 85% power to detect a dose-response model for ABBV-105 and combined placebo from 6 candidate models: Linear,

EMax (ED50 = 5 mg), Exponential ( $\delta$  = 20), Logistic (ED50 = 5 mg,  $\delta$  = 10), SigEMax (ED50 = 5 mg, h = 2), and Quadratic ( $\delta$  = -0.01) using MCP-Mod with one-sided significant level  $\alpha$  = 0.05.

The planned sample size of 60 patients treated with ABBV-599 provides approximately 94% power to detect a -1.0 difference in DAS28 (CRP) LS mean change from baseline for ABBV-599 vs the group of 40 patients treated with ABBV-105 (assuming ABBV-105 mean change from baseline: -1.65 and ABBV-599: -2.65 with common SD = 1.5) using two group t-test with one-sided significance level  $\alpha = 0.05$ . The sample size of 60 for ABBV-599 vs 20 for placebo is over-powered due to the necessary power for ABBV-105 over placebo.

The sample size of 60 patients for ABBV-599 vs 40 for upadacitinib could produce the half width of 0.5 in the two-sided 90% CI of the difference in mean change from baseline, assuming the common SD = 1.5. Assuming the observed difference for ABBV-599 vs upadacitinib is -0.45, the corresponding 90% confidence interval would be (-0.95, 0.05).

In the event that placebo variability precludes historic borrowing, comparison using only the in-study 20 placebo patients is estimated to still provide 68% power for pairwise comparison of ABBV-105 vs placebo and a minimum of 70% power in detecting a dose-response model for ABBV-105 and placebo.

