#### Mixed-Effect Model Repeated Measure (MMRM)

MMRM analysis will be conducted for repeated continuous measurements. Data collected after a subject discontinues study drug will be considered as missing. The mixed model includes the categorical fixed effects of treatment, visit and treatment-by-visit interaction, main stratification factors, and the continuous fixed covariate of baseline measurement. An unstructured variance covariance matrix will be used. The parameter estimation is based on the assumption of data being missing at random and using the method of restricted maximum likelihood (REML).

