#### Table 2.Subgroups for Primary Efficacy Analysis

## 9.0 Safety Analyses

## 9.1 General Considerations

Safety analyses will include reporting of adverse events, laboratory, and vital signs measurements. Safety analyses will be carried out using the Safety Analysis Set.

The following summary statistics will be presented for subjects who have both baseline and post-baseline values for laboratory parameters and vital signs: the mean value at Baseline and at each respective protocol specified visit, and the mean, standard deviation and median for changes from Baseline. Categorical data will be summarized using frequencies and percentages. The number of non-missing values will be given. Missing safety data will not be imputed.

A subject's actual treatment will be determined by the most frequent dose regimen received.

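### Adjusting the laboratory and vital-sign differences for baseline would give a modest, nearly free gain in precision over the planned ANOVA, which is valid as it stands

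*SAP*

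**What the plan says.** SAP 9.3 (laboratory data) states: "The change from baseline mean, standard error, and 95% confidence interval will be presented for the mean change from baseline within each treatment group". The same sentence goes on to the "difference between treatment groups using ANOVA model". SAP 9.4 repeats the sentence for vital signs. Neither section lists model terms, so the absence of a baseline covariate is read from the word ANOVA and from no covariate being named. Protocol 7.4 asks for mean change from baseline and names no model.

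Three other places bear on the point:

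- SAP 9.1 restricts these summaries to "subjects who have both baseline and post-baseline values for laboratory parameters and vital signs", so adjustment would lose no subject. It also has the baseline and visit means reported.
- The efficacy MMRM in SAP 8.2 includes "the continuous fixed covariate of baseline measurement", and SAP 8.3.5.1 does the same for DAS28 (CRP).
- SAP 9.3 rules out statistical tests after describing the shift tables. In context this does not withdraw the between-arm intervals.

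**The concern.** When the baseline value is known for every analysed subject, a comparison of raw change scores leaves precision unused. Change from baseline subtracts the whole baseline value, which over-corrects whenever the correlation between baseline and follow-up is below 1. Part of any chance baseline difference between arms then reappears in the estimate with the opposite sign (regression to the mean).

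The design makes this worth a look. Placebo has 20 planned subjects against 40 or 60 in the active arms. One placebo baseline mean serves all five active-versus-placebo comparisons and every visit. For 40 against 20, placebo supplies 1/20 = 0.050 of the baseline-difference variance of 1/40 + 1/20 = 0.075, or two thirds. A chance deviation in placebo would therefore push every comparison the same way. The variables also bear on named risks: protocol 2.2 lists anemia and lymphopenia for ABBV-105, and several laboratory abnormalities are adverse events of special interest in protocol 6.1. What is at stake is how sharply these descriptive comparisons can be read.

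**Working it through.** **Inputs.** The planned arms are 60, 40, 40, 40, 40 and 20 (SAP 2.3), 240 in total (SAP 2.4). If all subjects contribute, ANOVA has 240 − 6 = 234 error df, and adding baseline leaves 233. The correlation ρ between baseline and follow-up is not in the documents, so 0.3 to 0.9 is assumed, with equal SDs at the two times. Results are in units of that SD.

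**The plan's own figures.** The documents give none for the safety comparisons. The sample-size figures in SAP 2.4 ("with common SD = 1.5", one-sided 0.05) check the arm sizes only, and they reproduce with a noncentral t:

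- 40 vs 40, difference 0.88: 83.0% (stated 83%)
- 40 vs 20, difference 0.88: 68.2% (stated 68%)
- 60 vs 40, difference 1.0: 94.5% (stated 94%)
- 90% interval half-width, 60 vs 40: 0.50 to 0.51 (stated 0.5)

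**Precision.** Per-subject residual variance is 2(1 − ρ) for the change score and 1 − ρ² with baseline in the model. The ratio of interval widths is therefore √((1 − ρ²) / (2(1 − ρ))) = √((1 + ρ)/2). The 95% half-widths for 40 vs 20 are:

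- ANOVA: t(0.975; 234) × √(2(1 − ρ)) × √(1/40 + 1/20)
- Adjusted: t(0.975; 233) × √((1 − ρ²) × 234/233) × √(1/40 + 1/20)

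| ρ | 2(1 − ρ) | 1 − ρ² | (1 − ρ)² | Width ratio √((1 + ρ)/2) | Half-width, ANOVA | Half-width, adjusted |
|---|---|---|---|---|---|---|
| 0.3 | 1.40 | 0.91 | 0.49 | 0.806 | 0.638 | 0.516 |
| 0.5 | 1.00 | 0.75 | 0.25 | 0.866 | 0.540 | 0.468 |
| 0.7 | 0.60 | 0.51 | 0.09 | 0.922 | 0.418 | 0.386 |
| 0.8 | 0.40 | 0.36 | 0.04 | 0.949 | 0.341 | 0.324 |
| 0.9 | 0.20 | 0.19 | 0.01 | 0.975 | 0.241 | 0.236 |

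The adjusted interval is thus about 19%, 13%, 8%, 5% and 2 to 3% narrower. The percentages are the same for every pair of arms.

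**Imbalance.** The SE of a chance baseline difference for 40 vs 20 is √0.075 = 0.274 SD. A baseline difference D moves the ANOVA estimate by −(1 − ρ)D. For a one-SE imbalance the shift is 0.5 × 0.274 = 0.137 SD at ρ 0.5, 0.082 at 0.7 and 0.027 at 0.9. Relative to the SE of the ANOVA estimate this is √((1 − ρ)/2) = 0.50, 0.39 and 0.22.

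**Why these are one effect.** 2(1 − ρ) = (1 − ρ²) + (1 − ρ)². The last term is the variance of the leftover imbalance, shown in the fourth column. The planned interval already contains it, which is why the interval is wider.

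**Unequal SDs.** With baseline SD s0 and follow-up SD s1, the change-score variance exceeds the adjusted variance by (s0 − ρ·s1)². This is never negative. Apart from 1 df in 234, adjustment cannot widen the interval on average, but the percentages above no longer apply exactly.

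**Simulation check.** Six arms of the planned sizes, 3,000 runs at each ρ of 0.5, 0.7 and 0.9, contrast 60 vs 20:

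- Width ratios: 0.868, 0.924 and 0.977
- ANOVA coverage: 95.2%, 94.6% and 95.1%
- Slope of the estimate on baseline imbalance: −0.50, −0.28 and −0.11 for ANOVA; within 0.02 of zero once baseline was in the model

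**The case against.** The strongest reply is that nothing here is wrong. A change-score ANOVA in a randomized trial is unbiased, and the simulated coverage bears that out. No decision rests on these intervals: the ranked hypotheses in SAP 12.0 are efficacy tests, and no alpha, sample size or safety threshold depends on the laboratory or vital-sign models. The comparison with the efficacy MMRM carries limited weight, because that model supports the primary inference. Baseline means are reported beside the changes, so an imbalance would be visible. All of this stands, and it limits the point to an improvement.

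A reader might infer more: that the planned safety comparisons are biased, or that wide intervals and uncorrected imbalance are two separate harms. The documents and the arithmetic do not support either. The change score already uses the baseline value, the remainder is −(1 − ρ) times the imbalance, and its variance is inside the planned interval. What survives is a conditional point: in a trial that happens to be imbalanced, the unadjusted estimate is shifted by a predictable amount that adjustment would remove.

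The objection that ρ is unknown also stands. For variables with ρ at or above 0.7 the gain is about 8% or less. It does not remove the case for a change that costs so little.

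**Conclusion.** The point holds as a minor gain in precision, not as an error. SAP 9.3 and 9.4 plan a valid but less efficient estimate of the between-arm difference. Adjusting for baseline would narrow the 95% intervals by about 13%, 8%, 5% and 2 to 3% at correlations of 0.5, 0.7, 0.8 and 0.9, and would remove the part of a chance baseline difference that remains in a given trial. These sizes rest on an assumed correlation, equal SDs at baseline and follow-up, and the reading that ANOVA means treatment only.

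Because the main objective names safety beside efficacy, a reader might also infer that the trial's safety conclusions are at risk. The plan does not support that. Adverse-event summaries, rates of potentially clinically significant values, grade-shift tables and liver-threshold counts do not use this model.

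**What to change.** In SAP 9.3 and 9.4, keep the raw within-arm mean change, SE and 95% interval. Replace the between-arm part with an ANCOVA of change from baseline at each visit, with treatment as factor and that parameter's baseline value as covariate, and report the LS mean difference with its 95% interval. The word ANOVA should not simply be swapped for ANCOVA throughout the sentence. That would also turn the within-arm changes into adjusted means, which need not equal visit mean minus baseline mean as tabulated.

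The cost is SAP wording and one model term, with no new data and no subjects lost. There are two consequences to accept. Adjusted differences need not equal the difference of the raw within-arm changes, so a table footnote should say so. The model also assumes a common linear baseline slope, which may fit skewed laboratory measures less well. Protocol 7.1 has the SAP final before the Week 12 database lock, so the wording should be settled by then.
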